## **Statistical Analysis**

The sample size was based on the primary endpoint, ie delta in the time spent in range (TIR 70-180 mg/dl). To be able to detect a difference of 20% with 80% power at a 5% significance level with a two-sided paired t-test. Thirty-four participants should complete the study. To account a 40% attrition rate, we included a total of 40 participants in the study. The sample size was calculated using PASS 2020 software.

Data will be analyzed with the IBM SPSS software (IBM SPSS Statistics for Windows, Version 24;IBM Crop., Armonk, NY, USA, 2016). Categorical variables were assessed for frequency and percent. Continuous variables described as frequency and percent. Continuous variables were assessed for normal distribution using histogram and Q-Q plots. Normally distributed continuous variables were described as means and standard deviations (SD), and non-normally distributed parameters were described as median and interquartile rang (IQR). Categorical variables in the same group were compared using a dependent sample t test. Differences between groups in continuous data were compared using independent-sample t tests (normally distributed data) or Mann-Whitney test (skewed data). For variables that were non-normally distributed, the median interquartile range (IQR) were presented and Kruskal-Wallis test was applied to evaluate he differences.

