### **Methods:**

#### **Participants and study design**

Adolescents with T1DM will be enrolled at the Pediatric Endocrinology and Diabetes unit of the Edmond and Lily Safra Children's Hospital, Sheba Medical Center (Ramat Gan, Israel). Written informed consent was obtained from participants age  $\geq 18$  years or their parents or legal guardians if  $< 18$  years. Ethic approval and monitoring is obtained from the Helsinki Committee in Sheba Hospital.

The study design is a randomized, parallel assignment clinical trial without blinding (open label) due to the impracticality of blinding diets. The criteria for eligibility are: age between 12 to 22 years, presence of T1DM (according to the American Diabetes Association criteria) for at least one year, and usage of a CGMS (Dexcom, Medtronic, Libre) device. Exclusion criteria included medical history of eating disorders or any other mental illness.

Participants who will meet all inclusion criteria will be randomly assigned to either the intervention (LCD) diet group or to the MD group in a 1:1. Randomization assignments were computer generated by the study statistician prior to the start of the study using random permuted block sizes of 2 or 4.

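### The 80% power and 34 completers are tied to a paired t-test, but the primary comparison is between two independent parallel arms

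*Protocol*

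**What the plan says.** The Statistical Analysis section of the protocol names the quantity being sized: "The sample size was based on the primary endpoint, ie delta in the time spent in range (TIR 70-180 mg/dl". It then gives the operating characteristics: "To be able to detect a difference of 20% with 80% power at a 5% significance level with a two-sided paired t-test". The result follows: "Thirty-four participants should complete the study". The tool is also named: "The sample size was calculated using PASS 2020 software".

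Three other statements describe the comparison that this figure should serve:

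- The Hypothesis section sets the primary endpoint as a comparison of LCD with MD on CGM time in range (TIR).
- Participants and study design describes a randomized, parallel, open-label trial whose participants "will be randomly assigned to either the intervention (LCD) diet group or to the MD group in a 1:1" ratio. There is no crossover and no matching.
- Statistical Analysis gives the between-group test: "Differences between groups in continuous data were compared using independent-sample t tests (normally distributed data) or Mann-Whitney test (skewed data").

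**The concern.** A paired t-test needs two linked measurements on the same person or on matched persons. Here the LCD and MD values come from different, unmatched people. The natural pairing, baseline with follow-up, appears to be used up already in the delta. A paired test on TIR would ask whether TIR changed over time, not whether it changed more on one diet than on the other. So the test named for sizing conflicts with the endpoint, the design and the protocol's own between-group analysis.

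What is at stake is how the primary result can be read. If the 80% belongs to a within-person test, the power for the diet comparison could be far lower. The Hypothesis section starts from the premise that the diets have equal effect. A non-significant result would not prove that at any power, but with low power it would say very little, and the protocol would give readers no warning.

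**Working it through.** **Inputs from the protocol.** Two-sided 5% level, 80% power, difference of 20%, 34 completers, 1:1 allocation (hence 34 / 2 = 17 per arm). No SD is stated, and the text does not say whether 20% means absolute TIR points or a relative change.

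**Can 34 be reproduced?** Not directly, because there is no SD. It can only be back-solved. Write d for the difference divided by the SD of change, and use the noncentral t distribution:

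- paired test on n people: noncentrality d·√n, n − 1 degrees of freedom;
- two-sample test with m per arm: noncentrality d·√(m/2), 2m − 2 degrees of freedom.

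**Step 1. The d that gives 80% power under each way of reaching 34.**

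- (a) Paired, n = 34: d = 0.495 (noncentrality 0.495 × √34 = 2.89).
- (b) Paired within each arm, n = 17: d = 0.724 (0.724 × √17 = 2.98).
- (c) Two-sample, 17 per arm: d = 0.991 (0.991 × √8.5 = 2.89).

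**Step 2. Power of the two-sample comparison of LCD with MD at that d.** This assumes that the same 20% is the between-diet difference and that the same SD applies to change in both arms. The last two columns also take 20% as 20 absolute points.

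| Calculation behind 34 | d | Power, 17 per arm | Implied SD (20 / d) | Difference detectable with 80% power (0.991 × SD) |
|---|---|---|---|---|
| (a) Paired, n = 34 | 0.495 | 28.8% | 40.4 | 40.0 points |
| (b) Paired, 17 per arm | 0.724 | 53.5% | 27.6 | 27.4 points |
| (c) Two-sample, 17 per arm | 0.991 | 80.0% | 20.2 | 20.0 points |

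The powers depend only on d, so they are the same if 20% is relative.

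**Step 3. Does a round SD reveal which calculation was run?** With 20 absolute points:

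- SD 40 (d = 0.5), paired: power 0.795 at n = 33 and 0.808 at n = 34, so n = 34.
- SD 20 (d = 1.0), two-sample: power 0.781 at 16 per arm and 0.807 at 17 per arm, so 34 in total.

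Both give exactly 34. If 20% is relative, with an assumed baseline TIR of 50% (a 10-point difference), SD 20 paired and SD 10 two-sample again both give 34. The number does not identify the test.

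**Step 4. Power by assumed SD of change.** For a 20-point difference and 17 per arm, two-sample power is 96% at SD 15, 81% at SD 20, 62% at SD 25, 47% at SD 30 and 29% at SD 40.

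**Condition.** All these figures need 34 people to complete. The protocol plans 40 enrolled and 40% attrition, and 40 × 0.60 = 24, or 12 per arm. At 12 per arm, cases (a), (b) and (c) give about 21%, 40% and 64%. The attrition figure is a separate point and carries no weight here.

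**The case against.** The strongest reply is that the defect may be a single word. The planned between-group analysis already uses independent-sample tests, so the comparison itself and its type I error are unaffected. Since 34 is exactly what a two-sample calculation gives at d = 1.0, the run may have been right and only mislabelled. This stands: the mismatch is certain, the loss of power is not.

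Second, the 29% and 53% figures treat a within-person change as if it were the between-diet difference and carry over its SD. Neither step is in the protocol. That is correct, and the figures are therefore illustrations of scale.

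Third, delta is not defined and might mean the difference between diets. If so, a paired test fits even less well, because the two diets are given to different people.

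Fourth, the same section mentions a dependent-sample t test within a group (for categorical variables, as worded), which may be where the paired test came from. That may explain the wording, but a within-group test still does not supply power for LCD versus MD.

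Finally, the SD may be recorded in the PASS output or in an SAP that is not at hand. Its absence is accordingly not raised as a defect of its own. It matters only because the reader cannot resolve the mismatch without it.

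**Conclusion.** The point holds. As written, the 80% power and the 34 completers belong to a test that does not compare the two diets, so the protocol states no power for its primary comparison. This should be fixed.

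The consequence ranges from none beyond a wrong test name (two-sample calculation, power about 80%) to power of about 53% or 29% (paired calculation on 17 per arm or on 34). That range rests on 34 completers split equally, on d back-solved from 34, and on the same difference and SD applying between arms. The protocol does not show that the trial is underpowered, and it does not let a reader rule that out.

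**What to change.** Look up the saved PASS 2020 run before changing any wording.

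- **If it was two-sample:** correct only the test name, to a two-sided two-sample t-test on change in TIR between LCD and MD.
- **If it was paired:** do not carry the 80% over. Name the two-sided two-sample t-test for the primary comparison and restate, for two independent arms at the planned number of completers, either the power for the 20% difference or the difference detectable with 80% power.

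In both cases define delta, give the SD of change that was used, and say whether 20% is absolute points or relative.

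The cost is one look-up and one or two corrected sentences. The fix restates a figure and asks for no further enrolment. The drawback is that the restated power may be less favourable.

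### The sample-size figures do not reconcile: 40 enrolled with 40% attrition leaves 24 completers, not 34, and on that attrition rate the stated 80% power becomes about 64%

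*Protocol*

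**What the plan says.** The sample-size paragraph in the protocol's Statistical Analysis section ties the calculation to the primary endpoint: "The sample size was based on the primary endpoint, ie delta in the time spent in range (TIR 70-180 mg/dl"). The target is set out as "To be able to detect a difference of 20% with 80% power at a 5% significance level with a two-sided paired t-test". The number required is then given: "Thirty-four participants should complete the study". The next sentence makes the allowance for loss: "To account a 40% attrition rate, we included a total of 40 participants in the study".

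The Participants and study design section gives 1:1 allocation to the two diets. No other part of the protocol states a different attrition rate, enrolment or completer target. No standard deviation is given.

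**The concern.** The number of completers, the attrition rate and the enrolment are linked by simple arithmetic, so any two fix the third. Here they disagree by a margin that rounding cannot explain.

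The 80% power claim is attached to 34 completers. If the trial loses participants at the rate the protocol itself assumes, 40 enrolled will not deliver 34, and the claim does not describe the trial being run. This paragraph is the protocol's only justification for the trial's size. The Hypothesis section takes as its premise that the two diets have equal effect, so a null result from an underpowered comparison could easily be read as support for that premise.

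**Working it through.** **Inputs, all from the Statistical Analysis section unless noted.** Completers required: 34. Attrition: 40%. Enrolled: 40. Power 80%, two-sided 5%. Difference to detect: 20%. Allocation 1:1 (Participants and study design).

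**Step 1: try to reproduce the enrolment of 40.**
- Standard inflation, N/(1 − d): 34/(1 − 0.40) = 56.7, so 57, or 58 for equal arms.
- Common shortcut, N × (1 + d): 34 × 1.40 = 47.6, so 48.

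Neither gives 40.

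**Step 2: work back from 40.**
- Completers at 40% loss: 40 × (1 − 0.40) = 24, which is 10 fewer than 34.
- Attrition that links 40 to 34: 1 − 34/40 = 6/40 = 15%. Check: 34/0.85 = 40.

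**Step 3: power at 24 completers.** Without a standard deviation the 34 cannot be reproduced. The protocol's claim was therefore taken as given: the standardized effect was set to the value that yields exactly 80% power at 34 completers (noncentral t, two-sided 5%), and power was recomputed at 24. This was done for the paired test named in the sizing and for the independent-samples test named for group comparisons.

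| Test | Effect giving 80% at 34 | Power at 24 |
|---|---|---|
| Independent samples, 17 v 17 → 12 v 12 | d = 0.991 | 64.1% |
| Paired, n = 34 → n = 24 | d = 0.495 | 64.2% |
| Normal approximation, 17 v 17 → 12 v 12 | d = 0.961 | 65.3% |

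If 34 was only the smallest number reaching at least 80%, the true effect could be slightly larger. Calibrating at 16 per arm gives 66.9% at 12 per arm; calibrating the paired test at 33 gives 65.5% at 24. The range is therefore about 64% to 67%.

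**Step 4: detectable difference.** The effect detectable with 80% power at 12 v 12 is 1.21 times that at 17 v 17, and the ratio is the same for the paired test. So 20 becomes 20 × 1.21 ≈ 24, in whatever unit the protocol's 20% carries.

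**Step 5: dependence on the standard deviation.** The fall from 80% to 64% does not depend on it, because the effect is calibrated to the stated power. Absolute power does. As an illustration, assuming a 20-point difference, power at 12 per arm is 74% for an SD of 18, 65% for 20 and 57% for 22.

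**The case against.** The arithmetic is not in dispute, so the objections concern what is built on it.

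**The power loss is conditional.** It applies only if 40% is the intended rate and 34 completers really gives 80%. If 40% is a slip for 15%, power is unaffected. This stands, and the 64% must be read with that condition.

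**The completer number may be the wrong figure.** 24/0.60 is exactly 40, and 24 × 1.4 = 33.6 rounds to 34, so 24 might have been the true requirement, with 80% power intact. This is speculation: the protocol says outright that 34 should complete, and nothing in it supports 24. It is still a good reason to look at the original software output before rewriting the sentence.

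**The anchor is unverified.** The sizing names a "two-sided paired t-test", while the design has two parallel arms and the section elsewhere compares groups with independent-samples tests. The 64% is therefore a relative figure, not an estimate of this trial's absolute power. The near-identical results from the two tests follow largely from calibrating both to 80% at 34, and are not independent confirmation. This also stands. Which test should drive the sizing is a separate question that does not affect the mismatch.

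**Smaller points.** Twelve per arm assumes equal loss; a 16 v 8 split of the 24 gives about 59% under the same calibration. Participants who leave early may also contribute some glucose-monitoring data, so completers and analysed participants need not be the same. Neither point makes 34, 40% and 40 agree.

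**Conclusion.** The concern holds. The three figures 34, 40% and 40 cannot all be right, and neither the standard inflation formula nor the common shortcut reconciles them. This rests only on numbers printed in the protocol.

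On the protocol's own attrition rate, 24 participants complete. Power for the planned difference is then about 64% (up to 67% if 34 was rounded up), or equivalently the difference detectable with 80% power rises from 20 to about 24. This assumes that 34 completers gives 80% power, that 40% is the intended rate, and that losses are equal between arms. If the intended rate was 15%, the enrolment and power claim agree and only the rate is wrong. On either reading the sentence needs correction, because the justification for the trial's size relies on it.

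**What to change.** Check the original sample-size output to see which figure is wrong, then correct the sentence in one of two ways:

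- **If 40% is intended:** state that 40 enrolled is expected to yield 24 completers (12 per arm if losses are equal), with about 64% power for the planned difference, or 80% power for a difference of about 24 in the same unit as the planned 20.
- **If 40% is a slip:** change the attrition rate to 15%, the rate under which 40 enrolled gives 34 completers.

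Either way the cost is one corrected sentence, with no additional enrolment. Under the first option the stated power becomes less favourable; under the second, the allowance for loss becomes smaller.

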Composition, alteration, and diversity of the gut microbiota might affect the glycemic control. Dysbiosis and changes in the properties of the gut barrier have been documented in T1DM subjects. The common finding in all of these studies is the increased proportion of Bacteroides bacteria which appear at the time of the initial diagnosis and tend to decrease over time, but without reaching the levels of healthy children. According to a recent study in T1DM children, changes in diet directly influenced the intestinal microbiota composition, and therefore might correct the gut dysbiosis in patients with T1D. These results show the merit of studying the microbiome of already diagnosed T1D patients, with the prospect of performing microbiome interventions aimed at improving glycemic control.

We propose an integrated study examining the effect of the LCD versus the Mediterranean diet (MD) upon both the glycemic control and on the gut microbiome. In order to isolate the effect of intensive dietary intervention, we will compare LCD to MD. The MD has been widely reported as one of the healthiest models for preventing cardiovascular disease and beneficial

for HbA1c. The SEARCH Nutrition Ancillary Study concluded that a higher MD score was associated with better glycemic control and lipid profile in youth with T1D. To the best of our knowledge, this will be the first controlled study upon adolescents with T1D on a low carbohydrate diet.

According to most recent data reported, only a minority of individuals meet ADA ( American Diabetic Association) HbA1c goals and HbA1c levels remain particularly high in adolescents and young adults. Parents and patients who may consider LCD as an option to optimize glycemic control face many concerns including hypoglycemia, ketoacidosis, nutritional insufficiency, poor growth, inadequate bone mineralization, poor metabolic profile, and psychological consideration due to the lack of data. Because more patients are choosing to follow a carbohydrate-restricted diet, there is a need to evaluate benefits and risks of LCD vs. MD among youth with T1DM after consuming LCD.

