### Secondary end points

1. Evaluation of the influence of LCD vs. MD on HbA1c, insulin dose (average total daily dose/ kg), glycemic variability (TIR, Time below 54 mg/dl, CV- Coefficient Variant) and average blood glucose.
2. Assessment of the impact of dietary changes after an LCD vs. MD on gut dysbiosis.
3. Assessment of the impact of both diets on bone turnover measures, lipid profile, vitamin levels, weight and height.
4. Assessment of the impact of dietary changes after an LCD vs. MD on quality of life.

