#### *Glycemic control*

HbA1c was collected from blood samples at baseline, 12 and 24 weeks. Time spent in range (TIR) 70-180 mg/dl assessed by CGM was downloaded at each visit with the dietician. Severe hypoglycemia was defined as an episode requiring assistance and was confirmed by documentation of a blood glucose value less than 54 mg per deciliter.

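### The Statistical Analysis section assigns a within-group paired t test to categorical variables, names no between-arm test for them, and gives two conflicting summaries for continuous variables (minor, wording)

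*Protocol*

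**What the plan says.** All the test rules are in one paragraph of the protocol's Statistical Analysis section.

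- Description of categorical variables: "Categorical variables were assessed for frequency and percent".
- Test for categorical variables: "Categorical variables in the same group were compared using a dependent sample t test".
- Between-group tests: "Differences between groups in continuous data were compared using independent-sample t tests (normally distributed data) or Mann-Whitney test (skewed data".
- For non-normally distributed variables, after the median and IQR: "Kruskal-Wallis test was applied to evaluate he differences".

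Continuous variables are described twice. One sentence gives them frequency and percent. Two sentences later they get mean and SD if normally distributed, or median and IQR if not.

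The design (Participants and study design) is two parallel arms, low carbohydrate diet (LCD) and Mediterranean diet (MD), allocated 1:1. The Statistical Analysis section expects 34 completers.

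**The concern.** A dependent-sample t test works on the mean and SD of paired differences in a continuous measurement. A categorical variable with several unordered levels has no such difference. A yes/no variable can be coded 0/1 and forced through the test, but with few changes the t reference distribution is a poor approximation. The comparison is also misplaced: a within-arm test measures change from baseline in one diet group and says nothing directly about LCD against MD, which is the randomised contrast.

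The Introduction says that "there is a need to evaluate benefits and risks of LCD vs. MD among youth with T1DM after consuming LCD", so some risk data may well be reported as participants with or without an event. Severe hypoglycemia is a convenient example. The Glycemic control section defines it as an episode: "Severe hypoglycemia was defined as an episode requiring assistance and was confirmed by documentation of a blood glucose value less than 54 mg per deciliter". If it were summarised as yes or no per participant, the sentence on categorical variables is the rule that would apply. An analyst following it would run two separate within-arm tests, and a reader could take significance in one arm only as a difference between the diets.

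**Working it through.** **1. Which rule covers which data**

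| Type of data | Within one arm | LCD versus MD |
|---|---|---|
| Continuous, normal | none named | independent t test |
| Continuous, skewed | none named | Mann-Whitney (Kruskal-Wallis also named) |
| Categorical | dependent t test | none named |

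The dependent t test stands in the wrong row. Two readings are possible:

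- *As written:* categorical data have one test, of the wrong kind and for the wrong comparison, and within-group continuous change has none.
- *The word categorical is a slip for continuous:* the within-group test is then sensible, but the printed sentence misassigns it.

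Either way the sentence needs correcting. The conflict over how continuous variables are described is a separate slip in the same paragraph.

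**2. Does the choice of test change a result at this sample size?**

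The protocol gives no event counts or risks, so the counts here are assumed for illustration. Take n = 34/2 = 17 completers per arm, no participant with an event at baseline and k with an event on diet. The paired differences are k ones and 17 − k zeros.

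- Mean difference d = k/17; variance s² = 17·d·(1 − d)/16; t = d/√(s²/17) on 16 df.
- Exact McNemar: p = 2 × 0.5^k, because all k discordant pairs go one way.

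For k = 4: d = 0.2353, s² = 17 × 0.2353 × 0.7647/16 = 0.1912, t = 0.2353/√(0.1912/17) = 2.22, p = 0.041. Exact McNemar: 2 × 0.0625 = 0.125.

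| k of 17 | dependent t test | exact McNemar |
|---|---|---|
| 3 | 0.083 | 0.250 |
| 4 | 0.041 | 0.125 |
| 5 | 0.020 | 0.0625 |
| 6 | 0.009 | 0.031 |

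With 20 per arm (all 40 enrolled), k = 4 gives 0.042 against 0.125, so attrition does not drive the contrast.

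**3. Within-arm tests against the between-arm comparison**

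Suppose 4 of 17 on LCD and 3 of 17 on MD have an event, with none at baseline. The written rule gives p = 0.041 in one arm and 0.083 in the other. Fisher's exact test on 4/17 versus 3/17 gives p = 1.0.

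**4. Is the paired t test too liberal?**

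Enumerate every outcome at n = 17 with the same event risk r before and during diet and independent periods. Each participant then changes in either direction with probability r(1 − r).

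| Assumed r | False-positive rate, paired t | Exactly one of two arms significant, 2s(1 − s) |
|---|---|---|
| 5% | 0.8% | 2% |
| 10% | 3.3% | 6% |
| 15% | 4.8% | 9% |
| 20% | 5.0% | 9% |

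Here s is the rate in the middle column. The two-sided rate does not exceed 5% at any of these risks. Much of the gap in step 2 reflects how conservative exact McNemar is with 4 or 5 discordant pairs.

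**5. What a correct between-arm test could show**

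Fisher's exact test at 17 versus 17: 4 versus 0 gives 2 × C(17,4)/C(34,4) = 2 × 2380/46376 = 0.103, and 5 versus 0 gives 2 × C(17,5)/C(34,5) = 2 × 6188/278256 = 0.044. At least 5 versus 0 is needed for p < 0.05.

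**The case against.** The best defence is that this is a single wrong word. The next sentence turns to differences between groups in continuous data, so this one probably meant within-group change in continuous data, and another sentence in the paragraph is visibly misplaced. Apart from the microbiome data, the listed end points are continuous measures or scores. A test for other categorical data is commonly left to a statistical analysis plan, which is not at hand. Much of this stands: it makes the point minor, and the absence of a named categorical test is not by itself a fault. It does not rescue the sentence, which assigns a wrong test and would conflict with any plan that used a proper one.

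A reader might infer three stronger things, which the protocol does not support.

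- *That severe hypoglycemia has no valid analysis.* It is defined, but it is not a listed end point, and no sentence places it under the categorical rule; it could be analysed as a count or rate. Frequency and percent by arm is a valid description. Low glucose is also compared between the diets through a secondary end point, "glycemic variability (TIR, Time below 54 mg/dl, CV- Coefficient Variant) and average blood glucose", where time below 54 mg/dl is continuous and falls under the between-group tests. That measure does not capture episodes requiring assistance, but hypoglycemia is not left unexamined.
- *That the paired t test is too liberal for sparse yes/no data.* The p-values in step 2 suggest it; the enumeration in step 4 does not bear it out.
- *That equal diets would often look different.* Assuming zero events at baseline and an on-diet risk of 10%, 15% or 20% in both arms, exactly one arm is significant in 15%, 37% or 50% of trials. That builds in a real within-arm rise. It also needs a baseline record of the event, which the protocol does not schedule. With equal risk before and during diet, the figures are 6%, 9% and 9%.

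**Conclusion.** The point holds as a minor error in a stated analysis rule. The dependent-sample t test is assigned to categorical variables, it makes a within-arm comparison in a parallel-arm trial, and the between-group tests named cover continuous data only. The description of continuous variables contradicts itself in the same paragraph. These conclusions rest on the text alone.

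The size of any consequence cannot be fixed from the protocol. The p-values shown assume 17 per arm, no baseline events and chosen event counts. They show that the choice of test can move a result across 5%, not that it will. Any participant-level yes/no variable would be affected; severe hypoglycemia is an example only if it is summarised that way. The primary comparison of time in range is not touched.

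**What to change.** In the protocol's Statistical Analysis section:

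1. Reserve the dependent-sample t test, or the Wilcoxon signed-rank test for skewed data, for within-group change in continuous variables.
2. Compare categorical variables between LCD and MD with Fisher's exact test and, for yes/no variables, report the risk difference with a 95% CI.
3. Use the exact McNemar test for any within-group change in a paired yes/no variable.
4. Delete the sentence that describes continuous variables by frequency and percent, keeping mean and SD or median and IQR.

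The cost is wording only, with no new data, visits or participants. The drawback is that little can be shown by a test at this size. With about 17 per arm the intervals will be wide, and Fisher's test needs 5 versus 0 to reach p < 0.05, so the risk difference and its interval will be more informative than the p-value.

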### **Hypothesis:**

Since there are no previous studies comparing LCD vs. MD the premise is that the diets have equal effect with no superiority or inferiority.

Our Primary end point is to compare the impact of LCD and MD on the time in range (TIR) 70-180 mg/dl assessed by Continuous Glucose Monitoring (CGM) among adolescents with T1DM.

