#### *Glycemic variability*

Glycemic variability from continuous blood glucose monitoring (Libre, Medtronic, Dexcom) and included SD Time spent in range 70-180 mg/dl, Time between 70-54mg/dl, time under 54 mg/dl and CV (coefficient variant) assessed by CGM was downloaded at each visit (baseline, and weeks 1,2,4,7,10 and 12) with the dietician.

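### Delta TIR is compared between arms without a covariate, although baseline TIR is collected; with equal SDs and an assumed correlation of 0.4 to 0.9, adjustment is expected to cut the variance by about 28% to 2% (34 completers) or 26.5% to 0.3% (24)

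*Protocol*

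**What the plan says.** The Hypothesis section of the protocol states the aim as a comparison between arms: "Our Primary end point is to compare the impact of LCD and MD on the time in range (TIR) 70-180 mg/dl". The Statistical Analysis section makes the endpoint a change score: "The sample size was based on the primary endpoint, ie delta in the time spent in range (TIR 70-180 mg/dl").

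For comparing arms on continuous variables, that section says: "Differences between groups in continuous data were compared using independent-sample t tests (normally distributed data) or Mann-Whitney test (skewed data"). A Kruskal-Wallis test is also named for non-normal variables. No regression model and no covariate appears in the section.

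The sizing sentence names a different test: "To be able to detect a difference of 20% with 80% power at a 5% significance level with a two-sided paired t-test". It continues "Thirty-four participants should complete the study" and "To account a 40% attrition rate, we included a total of 40 participants in the study".

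The covariate is available. According to the Glycemic variability section, the CGM data, including TIR, "was downloaded at each visit (baseline, and weeks 1,2,4,7,10 and 12) with the dietician".

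**The concern.** A paired t-test compares two measurements on the same people. It cannot compare two parallel arms randomised 1:1. The sentence on between-group differences is therefore read here as the method for the primary comparison, because no other stated method fits it.

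A t-test on the change subtracts each participant's baseline with a slope fixed at 1. A linear model with baseline TIR as covariate estimates the slope from the data. Both target the same difference between diets, and both are valid under randomisation. The fixed slope is usually too steep when the correlation between baseline and follow-up is moderate, and it then adds baseline noise to the comparison. In a trial of 34 completers or fewer, precision available from data already in hand should not be given up without a reason.

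**Working it through.** **The protocol's own figures.** The 34 completers cannot be reproduced, because no SD is given. If the 20% is taken as 20 percentage points, 17 per arm with a two-sample t-test (two-sided 5%, 80% power) implies a standardised difference of 0.991, hence an SD of the change of 20/0.991 = 20.2 points. That SD is not needed below, since it cancels in the variance ratio. The stated 40% attrition from 40 enrolled leaves 40 × (1 − 0.40) = 24, not 34; 34 of 40 is a loss of 15%. Both sizes are therefore carried through.

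**Assumptions.** The protocol gives neither the correlation ρ between baseline and follow-up TIR nor the ratio k of follow-up SD to baseline SD. The range of ρ from 0.4 to 0.9 is assumed, first with k = 1 and then with k = 0.9 and 1.1. The arms are equal, with n per arm and N = 2n.

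**Formulas for k = 1, common SD σ**

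- t-test on change: Var = 2σ²(1 − ρ) × 2/n
- baseline-adjusted model: Var = σ²(1 − ρ²) × (2/n) × [1 + 1/(N − 4)], where the bracket is the expected price of estimating the slope
- ratio (adjusted to change) = (1 + ρ)/2 × [1 + 1/(N − 4)]

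The bracket is 1 + 1/30 = 1.0333 at N = 34 and 1 + 1/20 = 1.05 at N = 24.

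| ρ | Ratio, N = 34 | Reduction | Ratio, N = 24 | Reduction |
|---|---|---|---|---|
| 0.4 | 0.723 | 27.7% | 0.735 | 26.5% |
| 0.6 | 0.827 | 17.3% | 0.840 | 16.0% |
| 0.7 | 0.878 | 12.2% | 0.8925 | 10.8% |
| 0.8 | 0.930 | 7.0% | 0.945 | 5.5% |
| 0.9 | 0.982 | 1.8% | 0.9975 | 0.25% |
| 0.95 | 1.0075 | loss of 0.8% | 1.024 | loss of 2.4% |

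Break-even is at ρ = 2/1.0333 − 1 = 0.935 for N = 34 and 2/1.05 − 1 = 0.905 for N = 24. A simulation of 200,000 trials per setting gave reductions of 27.5% and 1.7% (N = 34) and 26.2% and 0.3% (N = 24) at ρ = 0.4 and 0.9, in agreement with the formula.

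**Unequal SDs.** The ratio becomes k²(1 − ρ²)/(1 + k² − 2ρk) × [1 + 1/(N − 4)].

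| k | N | ρ = 0.4 | ρ = 0.6 | ρ = 0.9 |
|---|---|---|---|---|
| 0.9 | 34 | 35.5% reduction | 26.6% reduction | 16.3% reduction |
| 0.9 | 24 | 34.5% reduction | 25.4% reduction | about 15% reduction |
| 1.1 | 34 | 21.0% reduction | 10.1% reduction | 3.3% loss |
| 1.1 | 24 | 19.8% reduction | 8.6% reduction | 5.0% loss |

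**Bound on the loss.** The denominator minus the numerator of the first factor is 1 + k² − 2ρk − k²(1 − ρ²) = (1 − ρk)², which is never negative. That factor is therefore at most 1 for any k and ρ. The expected loss cannot exceed 1/(N − 4), which is 1/30 = 3.3% at 34 completers and 1/20 = 5.0% at 24.

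**The case against.** The strongest case against is that nothing here is wrong. The change-score test is valid, the quoted sentence is a general one that names neither TIR nor a visit, and the choice of covariates is often left to a statistical analysis plan, which is not at hand. The benefit also rests on a correlation and an SD ratio that the protocol does not give. Across the assumed values the result runs from a 35.5% reduction to a 5.0% loss, and at correlations of 0.8 to 0.9 with equal SDs the gain is only 7% to 0.3%.

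Part of this stands. The link from the general sentence to the primary comparison is an inference. The gain is conditional and may be nil. The figures do not cover the Mann-Whitney branch. They also describe variance and not interval width: at 24 completers the larger t quantile after losing a degree of freedom multiplies the squared width by about 1.0055. At a correlation of 0.9 the ratio of 0.9975 then becomes about 1.003, a trivially wider interval.

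The objection does not remove the point. The protocol is not silent on the method: it names the between-group tests, and all of them are unadjusted. The possible loss is capped at a few percent, while the possible gain is several times larger.

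**Conclusion.** The concern holds as a recommendation on efficiency. The protocol fixes an unadjusted comparison of delta TIR although the natural covariate is collected. With equal SDs and a correlation between 0.4 and 0.9, adjustment is expected to reduce the variance of the diet difference by about 28% to 2% with 34 completers and 26.5% to 0.3% with 24. At a correlation of 0.6, the ratio of 0.827 makes 34 adjusted completers worth about 34/0.827 = 41 analysed by the change-score t-test, more than the 40 enrolled.

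The correlation range and the SD ratio are assumptions. No bias is alleged, and no particular gain in power or shift in the estimate is claimed.

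**What to change.** In the Statistical Analysis section, make the primary analysis a linear model of TIR at the primary visit (or the change to it, which gives the same diet difference) on arm, with baseline TIR as covariate. Report the adjusted difference between the low carbohydrate and Mediterranean arms with its 95% CI, and keep the unadjusted t-test or Mann-Whitney test as a sensitivity analysis. The text must also name the visit, since delta TIR is not tied to one at present.

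No new data are needed. The cost is a wording change and one degree of freedom. The variance price of the extra parameter, about 3% at 34 completers and 5% at 24, is already deducted in the figures above.
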